## 2 OBJECTIVES AND HYPOTHESES OF THE CLINICAL INVESTIGATION

### 2.1 Study Objectives

To evaluate the efficacy of VR101 as a personal lubricant for vaginal application, intended to increase vaginal lubrication and enhance the ease and comfort of intimate sexual activity.

### 2.2 Hypotheses of the Clinical Investigation

Compared to the sham device, a significantly greater proportion of participants who use VR101 for 4 consecutive weeks will experience increased vaginal lubrication that enhances ease and comfort of intimate sexual activity as assessed by the Lubrication domain of the FSFI (FSFI-LD  $\geq$  4.5).

## 3 ENDPOINTS

### 3.1 Primary Endpoint

The primary efficacy endpoint is the participant's score on the 4-item lubrication domain of the Female Sexual Function Index (FSFI) following 4 weeks of consecutive treatment with VR101 or a sham ring. The FSFI is a self-report survey validated to assess sexual function in women (Rosen, *et al.*, 2000; Wiegel *et al.*, 2005), supported by FDA as appropriate for evaluating VR101 efficacy. The FSFI contains 19 questions, divided in to 6 characteristic domains: Desire, Arousal, Lubrication, Orgasm, Satisfaction, and Pain. The Lubrication domain is directly relevant to the intended use for VR101. All participants admitted to the study will enter at a "dysfunctional" FSFI lubrication domain level. Following four weeks of treatment, participants with a score of 4.5 or better on the Lubrication domain will be considered "responders" and the proportion of responders in each group will be compared in the primary efficacy analysis.

J3 Bioscience, Inc.	Statistical Analysis Plan	CI03-SAP Rev. 00 Page 9 of 31
	CI03: A Clinical Investigation to Evaluate Efficacy of the J3 Bioscience Lubricating Intravaginal Ring VR101 as a Personal Lubricant Device in Women	

The FSFI Lubrication domain includes 4 questions:

- Q7. Over the past 4 weeks, how **often** did you become lubricated (“wet”) during sexual activity or intercourse? 0 = No sexual activity, 5 = Almost always or always, 4 = Most times (more than half the time), 3 = Sometimes (about half the time), 2 = A few times (less than half the time), 1 = Almost never or never
- Q8. Over the past 4 weeks, how **difficult** was it to become lubricated (“wet”) during sexual activity or intercourse? 0 = No sexual activity, 1 = Extremely difficult or impossible, 2 = Very difficult, 3 = Difficult, 4 = Slightly difficult, 5 = Not difficult
- Q9. Over the past 4 weeks, how often did you **maintain** your lubrication (“wetness”) until completion of sexual activity or intercourse? 0 = No sexual activity, 5 = Almost always or always, 4 = Most times (more than half the time), 3 = Sometimes (about half the time), 2 = A few times (less than half the time), 1 = Almost never or never
- Q10. Over the past 4 weeks, how **difficult** was it to maintain your lubrication (“wetness”) until completion of sexual activity or intercourse? 0 = No sexual activity, 1 = Extremely difficult or impossible, 2 = Very difficult, 3 = Difficult, 4 = Slightly difficult, 5 = Not difficult

Participants must answer these questions with a 1, 2, or 3 to be enrolled in the study at Visit 1. The upper bound of 3 ensures that all participants enter at a dysfunctional level of vaginal lubrication. After 4 weeks of consecutive use of VR101 or the sham IVR, it is expected that more of the participants in the VR101 group will have experienced a clinical degree of improvement in vaginal lubrication than those in the sham IVR group. In an FSFI cross-validation study (Wiegel *et al.*, 2005) a lubrication sub score threshold of 4.35 out of 6 was noted as an accurate discriminant of overall sexual dysfunction. The threshold for “responder” status for this study was set at 4.5 or greater because that is the next highest achievable score above 4.35. For lubrication domain scoring, responses to the four questions are summed and multiplied by a factor of 0.3. The lowest achievable FSFI-LD score for this study is 1.2 (as sexual activity is a required inclusion criteria, all 1 point responses,  $4 \times 0.3 = 1.2$ ) and the highest score is 6 (all questions answered at 5 points,  $20 \times 0.3 = 6$ ).

J3 Bioscience, Inc.	Statistical Analysis Plan	CI03-SAP Rev. 00 Page 10 of 31
	CI03: A Clinical Investigation to Evaluate Efficacy of the J3 Bioscience Lubricating Intravaginal Ring VR101 as a Personal Lubricant Device in Women	

### 3.2 Safety Endpoints

All adverse events (AE) and adverse device events (ADE) as well as any Serious AEs or ADEs will be recorded throughout the study and will be assessed for severity and relatedness to VR101 use. Each type of event is described, and examples are listed in the CI03 CIP.

### 3.3 Exploratory Endpoints

- Change in FSFI subdomain scores from screening to completion of 4 consecutive weeks of treatment with VR101 or the sham IVR. Point responses (numerical responses) for the set of questions for each domain are summed and then multiplied by the indicated factor for that domain. Individual domain scores at Visit 1 will be subtracted from individual domain scores at Visit 2 to provide a change score. The mean change from baseline for each of the domains will be compared across the study arms using Student's *t*-test.
- Change in total FSFI score from screening to completion of 4 consecutive weeks of treatment with VR101 or sham. Total FSFI reflects overall sexual function and is the sum of all domain scores. The mean change from baseline in total FSFI score will be compared across the study arms using Student's *t*-test.

## 4 STUDY PARTICIPANTS

### 4.1 Sample Size determination

As VR101's efficacy has not been tested using the FSFI-LD, power and sample size for this study were estimated using parameters gleaned from previous experience with VR101 (CI01 and CI02, described in detail in the CI03 CIP) and published literature on FSFI use in studies with similar populations. For the primary efficacy analysis, statistical comparison of the proportion of participants in each group with a FSFI lubrication domain score of 4.5 or better (responders) at the end of the 4 week treatment period, a Sham group (placebo) responder rate of 30% was used as a starting point for the sample size determination. Given the considerable uncertainty for variability of the FSFI-LD scores and expected proportion of responders in the VR101 group the sample size was based on 0.90 power to detect a minimum 60% response rate at  $\alpha = 0.01$ . Based on the power curves generated using this information and expected dropout rates of around 5%, it was determined that a minimum of 160 participants (minimum 80 each group) would need to be randomized to provide 0.90 power for the primary efficacy analysis.

J3 Bioscience, Inc.	Statistical Analysis Plan	CI03-SAP Rev. 00 Page 11 of 31
	CI03: A Clinical Investigation to Evaluate Efficacy of the J3 Bioscience Lubricating Intravaginal Ring VR101 as a Personal Lubricant Device in Women	

## 4.2 Procedures for Replacement of Participants

Participants may voluntarily withdraw from the investigation for any reason at any time. However, the participant must be queried as to their reason for withdrawal and, if consent has not been withdrawn an early termination visit scheduled for final FSFI and safety data collection, a pregnancy test if appropriate, and return of unused devices. As much detail as possible will be collected and the major reason for discontinuation will be recorded. Participants will not be replaced. All data collected from all participants will be reviewed prior to finalization of this SAP. Analysis groups and methods for addressing any missing data will be assigned and the final revision (00) of this SAP will be approved prior to unblinding.

## 4.3 Randomization and Blinding

All participants will receive a consecutive screening ID number upon signing the informed consent document. The screening numbers for each site (A and B) will start at 001 and run consecutively (001A through XXXA and 001B through XXXB). A binary computerized random number sequence will be generated for each site and consecutive subject numbers will be assigned to the random sequence (AR01 through ARXX and BR01 through BRXX). Screen failures will only have screening numbers assigned. Upon verification of inclusion and exclusion criteria each participant will be given the next unassigned consecutive subject number followed by their screening ID number as extension (for example, if the fourth person screened at Site A is the first person who meets all the study criteria their subject number would be AR01.004A.) Thus, each enrolled participant will have a unique subject number that identifies the site, the screening ID and the subject randomization and all participants who sign the informed consent document are accounted for in the subject disposition record.

## 5 DATA COLLECTION AND MANAGEMENT

Paper CRFs (Case Report Forms) will be used for data collection during the study. Paper CRFs will be printed on 2-part NCR (no carbon required) with a copy retained by the investigators at the conclusion of the study.

Data from CRFs will be transcribed into an electronic database by the sponsor using double data-entry following study opening. Since the hand-written original CRF copies will serve as the official study record, Sponsor/analyst bias does not present concern to the study, provided double data-entry and an additional, independent data audit of database transfer is performed.

J3 Bioscience, Inc.	Statistical Analysis Plan	CI03-SAP Rev. 00 Page 12 of 31
	CI03: A Clinical Investigation to Evaluate Efficacy of the J3 Bioscience Lubricating Intravaginal Ring VR101 as a Personal Lubricant Device in Women	

## 5.1 Interim Analysis

No interim analyses are planned. The double-blind random assignment will be secured by the sponsor until after study site data collection and database lock for the primary and exploratory endpoint data (FSFI scores and adverse events) are completed.

## 5.2 Deviations from the CIP

All deviations from the CI03 CIP will be recorded by study staff and assessed for potential impact on the primary outcome. Use of excluded concomitant medications, vaginal lubrication products, performance of oral sex prior to or during intercourse, and failure to attempt intercourse are considered protocol violations, with potential significant impact on FSFI-LD scores. Minor deviations include unavoidable out of window assessments and phone calls, ring use deviations, urine pregnancy tests conducted by mistake on participants who are not able to become pregnant and other events with little or no influence on the primary outcome. All deviations will be categorized and included (by treatment group) in a summary table for the final clinical study report.

## 6 STATISTICAL ANALYSES

The final Statistical Plan (SAP) will be completed prior to database lock and unblinding of the study data. Any deviations from the final analysis plan will be described and justified in the final clinical study report. Statistical analysis will be done using Minitab 19 Statistical Software (Minitab 2020).

### 6.1 Primary Efficacy Analysis

The planned primary efficacy analysis is a superiority comparison between the proportion of participants in each arm of the study who report FSFI-LD scores of 4.5 or better after using VR101 or the sham IVR for 4 weeks. This endpoint is assumed to reflect changes in FSFI-LD from baseline (Visit 1) to the study endpoint at Visit 2, 28 +/- 2 days later. The null hypothesis to be tested is that similar numbers of women in each of the study arms will report FSFI-LD scores of 4.5 or greater after 4 weeks of exposure to the study devices. The alternative hypothesis is that VR101 provides superior vaginal lubrication compared to the sham device. The planned test statistic is a simple test for the difference between two proportions,  $\alpha = 0.05$ , two-tailed test. Rejection of the null hypothesis will be interpreted as support for the alternative hypothesis, that there is a non-random superior effect on self-reported vaginal lubrication with use of the VR101 device compared to the sham device.

J3 Bioscience, Inc.	Statistical Analysis Plan	CI03-SAP Rev. 00 Page 13 of 31
	CI03: A Clinical Investigation to Evaluate Efficacy of the J3 Bioscience Lubricating Intravaginal Ring VR101 as a Personal Lubricant Device in Women	

The primary efficacy analysis will use a normal approximation test with separate estimates of the true proportion of responders in each arm of the study to calculate a Z score

$$Z = \frac{(\hat{p}_1 - \hat{p}_2) - d_0}{\sqrt{\frac{\hat{p}_1(1 - \hat{p}_1)}{n_1} + \frac{\hat{p}_2(1 - \hat{p}_2)}{n_2}}}$$

where  $p_1$  and  $p_2$  are the observed proportions of responders in each group and the confidence interval for the difference between the two proportions is given by

$$\hat{p}_1 - \hat{p}_2 \pm z_{\alpha/2} \sqrt{\frac{\hat{p}_1(1 - \hat{p}_1)}{n_1} + \frac{\hat{p}_2(1 - \hat{p}_2)}{n_2}}$$

where  $z_{\alpha/2}$  is the inverse cumulative probability of the standard normal distribution at  $1 - \alpha/2$ .

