5.3.5 Randomization and Blinding

Each enrolled subject randomly assigned in a 1:1 ratio to receive either VR101 devices or sham rings. A randomization schedule (separate for each site) will be prepared for treatment group assignment of each subject. The subject's randomization number will be

J3 Bioscience, Inc.	Clinical Investigation Plan and Protocol CI03	CI03-CIP Rev. 02 Page 28 of 60
	A Clinical Investigation to Evaluate Efficacy of the J3 Bioscience Lubricating Intravaginal Ring VR101 as a Personal Lubricant Device in Women	

unique. This number is not the same as the subject identification (ID) number which is assigned at the time of informed consent.

The subject ID number identifies the subject and consists of the site number plus subject number for that site. The randomization number identifies the treatment; the randomization schedule provides the correspondence between the subject ID number and the randomized treatment identification (VR101 or sham).

The trial will be double-blind, meaning the subject and Investigator/staff will not have access to or knowledge of the subject's treatment assignment. Further, since the Sponsor will create and securely maintain the randomization schedules, the Sponsor and Sponsor's representatives will not be made aware of a given subject's randomization number until the blind is broken. The Sponsor will ensure that the Study Monitor does not ever have access to the randomization assignments.

As this is a multi-site study, the study coordinator will monitor enrollment to ensure nominally equal representation of the 160 subjects across the sites, for example if two sites are selected, at least 1/3 of participants (53) would be enrolled at each site. Additionally, the Sponsor will create and securely maintain a separate randomization schedule for each site to ensure appropriate site representation in the study groups.

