8.7.3 Unavoidable Loss of Data

- It is understood that data may still be missing, for anticipated and unanticipated reasons (intercurrent events) that arise during the study. As no universally applicable methods for handling missing values are recommended in the guidance documents, methods for handling missing values in this study will be justified by reasons for missingness and predefined by updating this aspect in the statistical analysis plan during the blind review. An investigation will be made concerning the sensitivity of the results of analysis to the method of handling missing values.

It is expected that any study subject who begins one of the treatment arms following randomization will be included in the primary efficacy analysis. As noted, randomization criteria require all inclusion criteria are met and that screening (Day 0) FSFI-LD scores are complete. The primary efficacy outcome, proportion of subjects who have a “functional” score of 4.5 or more after 4 weeks of treatment, is therefore dependent on a post randomization FSFI-LD score.

- Where unavoidable, participants who cannot complete 28 days of treatment will be scheduled for an End of Treatment visit so that final FSFI-LD scores can be collected prior to withdrawal of consent.

J3 Bioscience, Inc.	Clinical Investigation Plan and Protocol CI03	CI03-CIP Rev. 02 Page 44 of 60
	A Clinical Investigation to Evaluate Efficacy of the J3 Bioscience Lubricating Intravaginal Ring VR101 as a Personal Lubricant Device in Women	

- For subjects who must drop out prior to providing study endpoint efficacy data the reason for early discontinuation will be ascertained and recorded in the CRF. Prior to data lock and unblinding of the randomization code the status and quality of each subject's study data will be assessed by the sponsor's data quality team. The disposition and assignment of each subject to a study population analysis group will occur prior to unblinding.
- Where final FSFI-LD data are not available and exceed greater than 5% of the values for comparison, a mixed model regression analysis that includes the dependent variable and one or more auxiliary variables that reflect plausible assumptions around the uncertainty due to missing data will be conducted and subjected to sensitivity analysis.

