### 8.3 Unavoidable Loss of Data

It is expected that any study subject who begins one of the treatment arms following randomization will be included in the primary efficacy analysis. As noted, enrollment in the study and randomization requires that all participants meet inclusion/exclusion criteria, including the Visit 1 FSFI-LD baseline. Initiation of treatment requires ability to independently place an IVR. The primary efficacy outcome, proportion of subjects who have a “functional” score of 4.5 or better after 4 weeks of treatment, is therefore dependent on a post randomization FSFI-LD score.

It is understood that data may still be missing, for anticipated and unanticipated reasons (intercurrent events) that arise during the study. As no universally applicable methods for handling missing values are recommended in guidance documents, methods for handling missing data in this study will be determined by the reasons for “missingness” and predefined by updating the SAP after blind review. Appropriate sensitivity analyses will be specified to evaluate assumptions associated with handling of all missing data.

Where unavoidable, participants who successfully start but cannot complete 4 weeks of treatment will be scheduled for an Early Termination visit so the final (Visit 2) FSFI-LD scores can be collected prior to withdrawal of consent.

For subjects who must drop out prior to providing study endpoint efficacy data, the reason for discontinuation will be ascertained and recorded in the CRF. Prior to data lock and unblinding the status and quality of each subject’s study data will be assessed by the sponsor’s data quality team. The disposition and assignment of each subject to a study population analysis group will occur prior to unblinding.

If final FSFI-LD are not available in excess of 5% of the unblinded data, mixed model regression that includes one or more auxiliary variables reflecting plausible assumptions around the uncertainty due to missing data will be conducted and subjected to sensitivity analysis.

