## 12 BLIND REVIEW SUMMARY TABLES

Table 1. Blind Review of Subject Completion, Protocol Deviations, and Analysis Subgroups by Site

	Site A (1)	Site B (2)	Total	Notes
Screened	116	105	221	
Screen Fail	26 (22.4%) Inc # 6            19 Inc # 5            1 Exc # 1            2 Exc # 5            1 Exc # 13           1 Exc # 13, 16      1 Inc # 4, Exc #1   1	19 (18.1%) Inc # 6            16 Inc # 5            1 Exc # 4            1 Inc # 4, Exc #1   1	45 (20.4%)	Expected screen fail was 30%
Randomized	90 (77.6%)	86 (81.9%)	176 (79.6%)	175 meet MITT criteria 1 Subject could not place ring so received no treatment and no post randomization measures were taken
Entered Treatment Phase	89	86	175	
Early Terminated	4 (4.5%)	5 (5.8%)	9 (5.1%)	ET final FSFI-LDs available for all.
Completed 4 weeks	85 (95.5%)	81 (94.2%)	166 (94.9%)	
Completed/ET with major protocol violations	6 (6.7%) Lube Use 4 Oral Sex 2	3 (3.5%) Lube Use 3	9 (5.1%)	
Completed/ET with other non-major protocol deviations	22 (24.7%)	33 (38.4%)	56 (32.0%)	
Completed/ET with no protocol violations recorded	61 (68.5%)	50 (58.1%)	110 (62.9%)	
Blind Review Data Quality Issues	2 (2.2%)	0 (0%)	2 (1.1%)	AR26 and AR 36

Table 2. Subject Demographics by Site

J3 Bioscience, Inc.	Statistical Analysis Plan	CI03-SAP Rev. 00 Page 23 of 31
	CI03: A Clinical Investigation to Evaluate Efficacy of the J3 Bioscience Lubricating Intravaginal Ring VR101 as a Personal Lubricant Device in Women	

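### The primary responder test ignores site and Visit 1 FSFI-LD; it is valid, but may give up precision that matters if the effect is smaller than planned

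*SAP*

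**What the plan says.** **Primary test.** SAP 6.1 states: "The planned test statistic is a simple test for the difference between two proportions", at two-sided alpha 0.05, as a Z statistic with a separate variance estimate for each arm. Protocol 8.1.1 plans the same kind of test. No covariate is named in either place. SAP 6.1 also says of the endpoint: "This endpoint is assumed to reflect changes in FSFI-LD from baseline (Visit 1) to the study endpoint at Visit 2".

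**Site.** Protocol 5.3.5: "the Sponsor will create and securely maintain a separate randomization schedule for each site to ensure appropriate site representation in the study groups". SAP 4.3: "A binary computerized random number sequence will be generated for each site". No block size is given.

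**Baseline.** Protocol 8.7.3: "randomization criteria require all inclusion criteria are met and that screening (Day 0) FSFI-LD scores are complete". Entry requires each of the four lubrication items to score 1 to 3 (SAP 3.1), so the domain score at entry lies between 4 × 0.3 = 1.2 and 12 × 0.3 = 3.6.

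**Other analyses.** Baseline enters the exploratory change scores only (SAP 3.3 and 6.2). SAP 9 moves the cut-off to 4.2 and 4.8, examines scores from 4.2 to 6.0, and puts women who could not place the ring back in the denominators. The one covariate model is conditional on missing data (SAP 8.3): "If final FSFI-LD are not available in excess of 5% of the unblinded data, mixed model regression".

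**The concern.** Two pre-randomisation variables are available for every randomised woman. One defines the randomisation schedules. The other is the baseline of the scale on which response is judged. If either predicts response, leaving it out makes the standard error of the risk difference larger than it need be.

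This matters because the trial passes or fails on this single comparison (protocol 8.5), and the SAP is candid about how little is known of the effect. It says that VR101 has not been tested on the FSFI-LD, and it refers to the position as "Given the considerable uncertainty for variability of the FSFI-LD scores and expected proportion of responders in the VR101 group" (SAP 4.1).

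The conditional mixed model does not fill the gap. SAP Table 1 shows 176 women randomised. One could not place the ring and has no post-randomisation measure. Nine terminated early, with the note "ET final FSFI-LDs available for all", and 166 completed four weeks. If the completers' scores are also present, which Table 1 implies but does not state, missing FSFI-LD is 1/176 = 0.6%, well below the 5% trigger.

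**Working it through.** **1. The plan's own sample size.** Inputs from SAP 4.1: 30% v 60%, alpha 0.01 (two-sided here), power 0.90.

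n per arm = [z₀.₉₉₅·√(2p̄(1−p̄)) + z₀.₉₀·√(p₁(1−p₁) + p₀(1−p₀))]² / (p₁−p₀)², with p̄ = 0.45

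= [2.576 × 0.7036 + 1.282 × 0.6708]² / 0.09 = 2.672² / 0.09 = 79.3, rounded up to 80.

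The stated 80 per arm reproduces, before any allowance for dropout.

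**2. Power of the stated test at its own alpha.** Exact binomial enumeration of the unpooled Z, two-sided 0.05. The 88/87 split is an assumed division of the 175 women who meet the modified ITT criteria.

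| Sham v VR101 | 80/80 | 88/87 |
|---|---|---|
| 30% v 64% (protocol 8.3) | 99.3% | 99.6% |
| 30% v 60% (SAP 4.1) | 97.2% | 98.2% |
| 30% v 50% (assumed) | 74.4% | 78.7% |
| 30% v 30% (type I error) | 5.18% | 5.27% |

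The unadjusted test therefore holds its level closely.

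**3. What adjustment could gain.** The documents do not say how strongly site or baseline predicts response, so these are ranges. Assumptions: correlation of 0, 0.3 or 0.5 between Visit 1 FSFI-LD (four items, each 1 to 3, times 0.3) and a latent Visit 2 scale; site gap in response of 0 or 15 points; unblocked 1:1 assignment; N = 160 or 175; 8,000 runs in each of 36 scenarios. The adjusted estimate is the standardised risk difference from a logistic model with arm, site and baseline, with an influence-function standard error.

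| Assumed correlation | 0 | 0.3 | 0.5 |
|---|---|---|---|
| Variance, adjusted / unadjusted | 0.98–1.02 | 0.93–0.96 | 0.83–0.85 |
| Adjusted power, 30% v 60% (unadjusted 97–98%) | 97–98% | 98–99% | 99% |
| Adjusted power, 30% v 50%, N = 160 (unadjusted 74–75%) | 74–75% | 77–78% | 82% |
| Adjusted power, 30% v 50%, N = 175 (unadjusted 78–79%) | 78–79% | 81% | 85% |

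Site alone gives a variance ratio of 0.97–1.01. Simulated type I error is 5.1–5.6% adjusted and 5.0–5.6% unadjusted.

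**4. Hand check of one cell.** For 30% v 50% with 87.5 per arm, SE = √[(0.21 + 0.25)/87.5] = 0.0725.

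- Unadjusted: Φ(0.20/0.0725 − 1.96) = Φ(0.80) = 0.79.
- Variance ratio 0.85: Φ(0.20/(0.0725 × √0.85) − 1.96) = Φ(1.03) = 0.85.

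Both agree with the table.

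**5. A second parametrisation.** N = 175 (89 and 86 by site), arms balanced within site, normally distributed baseline, 3,000 runs per setting, 30% v 50%. A baseline log-odds ratio of 0.5 per SD cuts variance by about 4–5% and adds about 3 points of power. At 1.0 per SD the cut is about 14–17% and the gain about 7 points. A site effect alone (log-odds ratio up to 1.0) changes power by about 1 point or less.

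**The case against.** The strongest reply is that nothing here is an error. The planned test holds its type I error, and at the planned effect adjustment is worth about 1 point of power. The sample size was set at alpha 0.01 while the test runs at 0.05, and 176 women were randomised against a minimum of 160. With 88/87 the exact power is still 92.5% at a VR101 rate of 55% and 90.5% at 54%, so the true rate must fall some 6 points below the SAP's 60% before power nears 90%. All of that stands, and it is why this is an improvement and not a correction.

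Second, site adds almost nothing. That also stands. The usual reason to include it is that it defines the randomisation schedules, and with no blocking stated even that reason is weak.

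Third, baseline is handled by design. Nobody enters above 3.6, so every responder has gained at least 4.5 − 3.6 = 0.9. This answers any doubt that response means improvement, but not the question of precision: women entering at 1.2 and at 3.6 may still differ in their chance of reaching 4.5. The narrow entry range may weaken baseline as a predictor. The main simulation includes that range, but the correlation itself is assumed.

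Fourth, SAP section 1 says that section 10 holds revisions made after the blind review, and SAP 10.4 and Table 3 were not available. An adjustment specified there would settle the point.

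Fifth, replacing the pass/fail test after data collection is a large step for an uncertain gain. It is acceptable only while the data are blinded. The SAP's own process allows revision up to that time (SAP 4.2 and 6).

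**Conclusion.** The concern holds as a point about efficiency. The responder comparison uses neither the variable that defines the randomisation schedules nor the baseline of its own scale, and no visible analysis supplies the adjustment. The loss is negligible in power terms at 30% v 60%. At an assumed 30% v 50% the adjusted analysis gains from nothing (correlation 0) to about 6 to 8 points (correlation 0.5), almost all of it from Visit 1 FSFI-LD.

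The correlation, the site gap and the 50% rate are assumptions. Any precision lost is lost at every effect size; only its consequence for power depends on the effect being smaller than planned. Confidence is medium because the size of the gain cannot be learned from the documents and part of SAP section 10 was not seen. The change is worth making while blinded, because the data are already collected and the worst case is small.

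**What to change.** Before unblinding, replace the test in SAP 6.1 with text along these lines: *The primary analysis is a logistic regression of responder status on arm, site and Visit 1 FSFI-LD (continuous), reported as the standardised difference in responder proportions, VR101 minus sham, with a two-sided 95% CI from a robust standard error. The endpoint is met if the lower limit is above 0. The simple two-proportion comparison is a sensitivity analysis.*

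Change protocol 8.1.1 to match, and have protocol 8.5 say which analysis decides success; its 95% criterion is otherwise unaffected. Protocol section 10 requires sponsor and IRB approval for a change to the data analysis. Confirm that Minitab 19, named in SAP 6, can produce the standardised difference and its standard error, or name another package.

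The cost is this wording, the approvals and a few lines of analysis; no new data are needed. The statistical downside is a variance increase of at most about 2% if baseline does not predict response. If the sponsor prefers to leave the primary test alone, pre-specifying the adjusted difference as supportive would still give a potentially more precise estimate, but no gain in the chance of passing.
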